Title: Assessing the Cortical Response to Noxious and Auditory Stimuli Using Near Infrared Spectroscopy in Subjects under General Anesthesia

NCT: NCT02703090

Date: May 22, 2018

Title: Assessing the Cortical Response to Noxious and Auditory Stimuli Using Near Infrared Spectroscopy in Subjects under General Anesthesia

Research Question: To determine the utility of functional near infrared spectroscopy (fNIRS) in the objective, quantitative assessment of nociception and anti-nociception (analgesia) in patients under general anesthesia. A secondary question is the use of fNIRS to measure actual or intended movement either spontaneously, in response to pain, and/or in response to auditory stimuli during general anesthesia.

Significance: This study is part of an ongoing project to determine the value of fNIRS/DOI as a tool for measurement of nociception and anti-nociception and monitoring depth of anesthesia to prevent awareness and pain in patients under general anesthesia. NIRS/DOI is capable of continuously monitoring and tomographically imaging changes in oxy- and deoxyhemoglobin concentrations as a result of noxious stimulation.

Design: Prospective cohort study.

Subjects: Pediatric and adult subjects 12-30 years of age (ASA physical status I or II) undergoing routine electrophysiology procedures in the cardiac catheterization laboratory at Boston Children's Hospital will be eligible for enrollment. We plan to study and obtain useful data sets in 45 subjects with structurally normal hearts undergoing catheter ablation of arrhythmias under planned general endotracheal anesthesia.

Parents/guardians of eligible children and adults will be approached for enrollment at the pre-catheterization evaluation

Variables: Changes in oxyhemoglobin and deoxyhemoglobin concentrations measured by NIRS. Functional NIRS, also known as diffuse optical imaging (DOI), will be used to measure (1) the hemodynamic activations in the bilateral somatosensory cortices and the prefrontal cortices in response to the noxious stimulation (pain) associated with catheter ablation of arrhythmias, and whether these activations are reduced or eliminated by remifentanil, and (2) the hemodynamic activations in the supplemental motor area to actual or intended movement either spontaneously, in response to pain, and/or in response to auditory stimuli.

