Statistical Issues: In our pilot study, we were able to collect useable data from five of the eleven subjects that were enrolled (45%). In the five subjects that produced usable results, the signal of interest had a mean value of -3.764×10^{-7} Moles with a standard deviation of 2.135×10^{-7} Moles. This results in a standardized effect size of 1.763, when using a zero mean for the null case. In order to achieve a 90% power level for this measure, the number of usable data sets is therefore eight. Considering our previous success rate of 45%, approximately 18 subjects will need to be enrolled into each group of the study for a total enrollment of 54 subjects. The data analysis will first be performed on a within-subject basis. Then, the original raw optical time series will be averaged across subjects (for corresponding optode placements only, standardized relative to the EEG 10-20 system).

1. Specific Aims /Objectives

The primary aim is to utilize near-infrared spectroscopy (NIRS) in patients under general anesthesia to measure hemodynamic activations in the bilateral somatosensory cortices and the prefrontal cortices in response to the noxious stimulation (pain) associated with catheter ablation of arrhythmias. Randomization of patients to placebo or one of two opioid doses should allow for discrimination between cortical activation and scalp sympathetic changes in response to pain.

Secondary aims are to utilize NIRS to measure hemodynamic activation in the supplemental motor area to actual or intended movement either spontaneously or in response to pain, and in the auditory cortices in response to auditory stimuli.

This study is part of an ongoing project to determine the value of NIRS as a tool for measurement of pain during general anesthesia and to monitor depth of anesthesia in order to prevent awareness.

2. Background and Significance

Anesthesia is a state of drug-induced unconsciousness with suppression of sensory perception, differing from normal sleep by the intensity of stimulus required to awaken the brain to conscious perception. Anesthesia can be defined by hypnotic (unconsciousness) and analgesic (pain relief) components, so that clinical anesthesia involves the administration of hypnotic and analgesic agents with the anesthesiologist observing the clinical response to noxious stimuli and adjusting the dosage to achieve an adequate depth of anesthesia.

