is capable of continuously monitoring and tomographically imaging changes in oxy-and deoxyhemoglobin concentrations during somatosensory stimulation, such as finger tapping, finger tactile, and electrical median nerve stimulation (Becerra, Harris et al. 2008, Minati, Jones et al. 2009, Nambu, Osu et al. 2009) and multiple applications in children (Wolf and Greisen 2009, Watanabe, Homae et al. 2010). We have also shown with fMRI studies that pain stimulation activates sensory areas. Our group has a great deal of experience performing DOI measurements simultaneously with fMRI, and have demonstrated that the functional signals measured with DOI correlate temporally with fMRI signals (Strangman, Culver et al. 2002).

In our previous work using the same approach we have shown that an acute thermal stimulus using an FDA-approved Peltier thermode produces significant and measurable effects that can be measured in a number of cortical regions in healthy volunteers (Becerra, Harris et al. 2008). We have not completed the work on simultaneous fMRI and DOT measures in healthy subjects and this continues under an approved IRB protocol at MGH, 2007-P-000270, entitled “Assessing the Cortical Response to Painful Stimuli with Diffuse Optical Imaging”.

4. Design and Methods

a. Study Design

General Procedures

We plan to study and obtain useful data sets in 45 subjects (12-30 years of age) scheduled for elective electrophysiology procedures in the cardiac catheterization laboratory and undergoing ablation of arrhythmias under planned general endotracheal anesthesia. As a number of subjects may choose to withdraw from the study following enrollment, and because some subjects will not be able to participate in the study if it is not possible to obtain adequate NIRS signals (as discussed below under Study Procedure: Day of Surgery), we plan to enroll 54 subjects to allow for drop-outs.

- **Pre-Operative Visit**

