d. Statistical Power and Sample Considerations

In our pilot study, we were able to collect useable data from five of the eleven subjects that were enrolled (45%). In the five subjects that produced usable results, the signal of interest had a mean value of -3.764×10^{-7} Moles with a standard deviation of 2.135×10^{-7} Moles. This results in a standardized effect size of 1.763, when using a zero mean for the null case. In order to achieve a 90% power level for this measure, the number of usable data sets is therefore eight. Considering our previous success rate of 45%, approximately 18 subjects will need to be enrolled into each group of the study for a total enrollment of 54 subjects.

e. Study Organization

The principal investigator for this study is [name], MBBCh in the Department of Anesthesiology, Perioperative and Pain Medicine at Boston Children’s Hospital. The Research Nurse(s), Study Coordinator ([name] MPH), and co-investigators ([name] MD, and [name] PhD) are members of the Department of Anesthesiology, Perioperative and Pain Medicine at Boston Children’s Hospital. Other co-investigators ([name] MD) and ([name] PhD) are members of the Department of Cardiology at Boston Children’s Hospital and Martinos Center for Biomedical Imaging, Department of Radiology, Massachusetts General Hospital), respectively. Members of the P.A.I.N. research group will participate in data collection and data analysis.

f. Data and Safety Monitoring Plan

Confidentiality will be ensured by assigning anonymous subject identification codes to each subject. The subject-screening log, which lists the names corresponding to the subject identification codes, will be kept on a locked computer, access to which is limited to only one investigator.

The risk posed to the subject in this study is minimal. Subjects will have the right to discontinue the study at any time prior to induction for any reason. Also, investigators will be in the room ready to stop the experiment in case there is any sort of adverse event. After induction of anesthesia the attending anesthesiologist and/or cardiologist may discontinue the experiment if clinical conditions warrant or in the case of an adverse event. Adverse events will be reported to the IRB as indicated above.

The investigators will review the data after the first 5 subjects and then after every 10 subjects to ensure that adequate data is being obtained.

6. Risks and Discomforts

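### The plan promises 45 useful data sets from 54 enrolled (83%), but it derives the same 54 from a 45% usable rate, which yields about 24

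*Combined protocol and SAP*

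**What the plan says.** Two parts of the document give a target for usable data, and two parts derive the enrolment.

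- **Synopsis, Subjects:** "We plan to study and obtain useful data sets in 45 subjects with structurally normal hearts".
- **Section 4.a, General Procedures:** the same target, "We plan to study and obtain useful data sets in 45 subjects". The section then gives two reasons for enrolling more: subjects may withdraw, and "some subjects will not be able to participate in the study if it is not possible to obtain adequate NIRS signals". It concludes: "we plan to enroll 54 subjects to allow for drop-outs".
- **Synopsis, Statistical Issues, and section 5.d (same text in both):** the pilot gave usable data in five of eleven enrolled subjects, stated as 45%. For 90% power, "the number of usable data sets is therefore eight". Then: "Considering our previous success rate of 45%, approximately 18 subjects will need to be enrolled into each group of the study", for a total of 54.

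The figure 45 is not derived anywhere, and no section states an expected usable rate other than the pilot's 45%.

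**The concern.** One enrolment figure carries two incompatible yields. Section 4.a treats 54 as enough to deliver 45 useful data sets after all losses. Section 5.d treats 54 as what is needed to deliver 8 per group, or 24 in all. Both run from enrolment to usable data: section 4.a names signal failure among its losses, and the pilot rate has enrolled subjects as its denominator. They therefore cannot be read as successive stages of attrition.

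A reader of the synopsis or design section would expect nearly twice the data that the statistical section plans for. A final count near 24 would look like a serious shortfall against 45, although it is what section 5.d anticipates. Section 5.f schedules reviews of whether adequate data are being obtained, and the document leaves two different benchmarks for that judgement.

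**Working it through.** **Inputs**

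- Target useful data sets: 45 (synopsis, Subjects; section 4.a)
- Enrolment: 54 (section 4.a; Statistical Issues; section 5.d)
- Usable data sets needed per group: 8 (Statistical Issues; section 5.d)
- Pilot usable rate: 5/11 = 45.5%, stated as 45% (same places)
- Groups: 3

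**Reproducing the plan's enrolment**

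- Per group = usable needed / usable rate = 8 / 0.45 = 17.8, rounded up to 18. With 5/11 it is 17.6, also 18.
- Total = 3 × 18 = 54. This matches the plan exactly.

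**Yield implied by each statement**

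| | Section 4.a | Section 5.d |
|---|---|---|
| Enrolled | 54 | 54 |
| Usable rate | 45/54 = 83.3% | 45% (5/11 = 45.5%) |
| Usable, total | 45 | 54 × 0.45 = 24.3; 54 × 5/11 = 24.5 |
| Usable per group (equal split) | 15 | 18 × 0.45 = 8.1; 18 × 5/11 = 8.2 |
| Losses | 54 − 45 = 9 | 54 × 0.55 = 29.7; 54 × 6/11 = 29.5 |

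Ratio of the two totals: 45/24.5 = 1.84.

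**Enrolment needed for 45 usable at the pilot rate**

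45/0.45 = 100, or 45/(5/11) = 99.

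**Per-group enrolment if the yield really were 83%**

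8/0.833 = 9.6, so 10 per group. Eighteen per group would correspond to 18 × 0.833 = 15 usable.

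**Uncertainty in the pilot rate**

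- The exact (Clopper–Pearson) 95% interval for 5/11 is 16.7% to 76.6%. Applied to 54 enrolled, the expected usable count runs from about 9 to about 41.
- If the true rate were 5/11, the binomial probability of 45 or more usable out of 54 is about 1 × 10⁻⁸.
- Allowing for the pilot's size (beta-binomial, uniform or Jeffreys prior on the rate), that probability is about 0.6%.

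**Precision relative to the stated target**

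With equal groups and the same SD, the standard error of a group mean at 8 rather than 15 usable is larger by a factor of √(15/8) = 1.37, or 37%.

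**The case against.** The best defence is that this is a loose descriptive number with little consequence. The study is sized on 8 usable per group, and the enrolment of 18 per group is consistent with that. No inference is based on 15 per group, so against the actual power basis no precision is lost. This stands, and it limits the finding: the usable sample size is misstated, but the power calculation does not fail because of it. The 37% figure measures the gap from the stated target only.

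A second argument is that 45 is a hope and 45% a cautious planning rate, and that the two can coexist. Several features could raise the yield: the CW 7's signal-quality features (section 2), cap repositioning and signal testing before induction (section 4.a), exclusion of subjects whose scalp or hair blocks light (section 4.b), and recruitment of patients likely to undergo ablation (section 4.c). A better yield than the pilot's is plausible, but none of these comes with a figure, and the statistical section still plans on 45%. Section 4.a also presents 54 as the enrolment chosen to allow for losses from 45, not as a cautious bound.

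A third point is that useful data sets are not defined, and might include the auditory or motor-area recordings, whereas the pilot rate concerns one signal of interest. This is possible but unstated, and it leaves the two numbers unreconciled.

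Finally, the pilot is small. The 41 of 54 at the upper confidence limit is an expected count, not a ceiling: at a true rate of 76.6%, 45 or more would occur about 16% of the time. The 10⁻⁸ probability treats 5/11 as exactly known, so the 0.6% figure is the fairer one. Either way, 45 is not what the plan's own rate predicts.

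**Conclusion.** The inconsistency is real and should be corrected. The synopsis and section 4.a state a usable sample of 45 (83% of 54), while the plan's own usable rate gives about 24 (about 8 per group). The difference is about 20 data sets, with 29 to 30 expected losses against the 9 allowed for. The figure without support is 45; the 54 enrolled and 8 per group are mutually consistent.

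The size of the gap rests on the 45% rate that the plan uses and, for the per-group figures, on an equal split across three groups. The direction does not depend on the rounding of 5/11, and even the upper 95% limit of the pilot rate gives an expected count below 45. This conclusion does not address whether 8 per group is itself an adequate basis for the comparisons planned.

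**What to change.** In the Subjects paragraph of the synopsis and in section 4.a, replace the target of 45. Suggested wording: *We plan to enroll 54 subjects (18 per group). At the pilot usable rate of 45% we expect about 24 useful data sets (about 8 per group).* Section 4.a should add that this rate is per enrolled subject, so it already counts any loss after enrolment, whether from withdrawal or inadequate signal. The document does not say why six of the eleven pilot subjects failed, so the sponsor should confirm that the pilot's losses were of these kinds. If 45 was meant as the number of subjects studied, say so and give the expected useful number separately.

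This costs wording in two places. Enrolment, the Statistical Issues paragraph, section 4.c and section 5.d stay as they are. The only downside is a less favourable stated number.

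Keeping 45 costs more, by either route:

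- **45 from 54:** the Statistical Issues paragraph and section 5.d must state and justify a yield near 83%, above the pilot's upper limit of 77%, and re-derive the per-group number, since 8 usable would then need only 10 enrolled per group.
- **45 at the pilot rate:** enrolment rises to 99 to 100, about 45 more patients, with changes to the Statistical Issues paragraph and sections 4.a, 4.c and 5.d. The 8-per-group basis does not call for these patients.

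Optionally, the reviews in section 5.f could compare the pooled, arm-blind usable count with the planning rate. If subjects are counted from enrolment, about 15 × 5/11 = 6.8 usable would be expected after 15 subjects and 25 × 5/11 = 11.4 after 25. This is not needed to resolve the contradiction.

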The pre-operative visit for electrophysiology procedures typically takes place in the cardiac pre-operative clinic 1-2 days before the date of catheterization. For patients currently in hospital, evaluation and recruitment will take place on the ward, typically the day prior to the procedure. At this visit, the Principal Investigator, an Anesthesia Research Nurse, and/or an Anesthesia Research Coordinator will present the study to the subject or to the parent/guardian and child (if the subject is a minor). At this time, consent and child assent when appropriate will be obtained. Following consent/assent, a Pre-Operative Questionnaire (Appendix B) will be filled out by the subject. This questionnaire asks study-relevant questions, such as hair color and thickness, and questions regarding demographics and subject contact information. If preferred, the subject may take the questionnaire home to fill out and return it to the study staff prior to the procedure.

After consent has been obtained, the subject will be assigned a study identification number and randomized to receive during the procedure normal saline infusion (placebo; i.e. no remifentanil)

[figure not shown]
or to one of two remifentanil infusion regimens. The study subject and investigators analyzing the NIRS signals will be blinded to this information.

- Day of Surgery

Before the Procedure:

First, the subject will be rebriefed on the nature of the study and of the experimental paradigms. Subjects will have the option of withdrawing from the study prior to administration of sedation and anesthesia.

Following light sedation with midazolam and prior to induction of general anesthesia, study personnel will position the probe holding the fiber optics (“optodes”) on the subject’s head. The optodes are contained in a cap (shown below). The cap is not constricting, and any discomfort will be minimized by surrounding the optodes with foam tape and using soft cloth straps against the head, face and chin. After initial positioning, the cap may need to be shifted slightly until adequate signals are obtained through all detector fibers. The fibers are 1-3mm in diameter, allowing them to be easily wiggled through the hair to make optical contact with the scalp. In some cases, hair will be parted in order to achieve better optical contact. No shaving of hair will be necessary or performed.

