Prior to the induction of general anesthesia, we will perform the following to test optode placement and signal quality:

1. Resting state data will be collected for about 200 seconds while the patient is quietly lying still. This baseline data will be used to compare changes observed during the catheterization procedure.
2. Auditory Stimuli: Headphones will be placed on the subject's head and an audio recording will be presented to the subjects. This data will be used as baseline consciousness data, as well as to familiarize the subject with the study procedures. In order to activate the Supplemental Motor Area (SMA), which should be quiet unless patients move, we will adapt a previously employed method for evaluating subjects in the vegetative state (Owen, Coleman et al. 2006). The auditory stimulus will be presented for 5 seconds, with a varied inter-stimulus interval. The prompt will request that the subject imagine squeezing a tennis ball in their right hand in a clasping motion, without actually performing the action. During this we expect SMA activity to occur if the subject is consciously aware.
3. . The subject will be asked to perform a brief finger tapping exercise, tapping the fingers of the left hand against the thumb for 5 seconds, with 15 seconds between, for 5 cycles. This will only be conducted if time permits.
4. . Brush stimuli will be applied to the dorsum of the left hand in a similar manner. This will only be conducted if time permits.

4.

A BIS (Bispectral Index) monitor will be used in all study patients in order to control the depth of anesthesia. A BIS sensor will be placed on the forehead and a BIS value between 40 and 60 will be targeted. A BIS <60 is advocated to prevent awareness during general anesthesia (Avidan, Zhang et al. 2008). This will also allow for reduced variability in the depth of anesthesia between the subjects during the ablations.

During the Procedure:

The audio stimuli will be presented to the subject every half hour throughout the procedure. Near-infrared signals are measured and recorded by the NIRS device (TechEn CW 7) throughout the procedure and will not influence the procedure.

The anesthetic technique will be standardized for all study subjects, and will comprise the following:

Premedication: Midazolam 0.05 mg/kg IV up to a maximum of 2 mg
Induction: Fentanyl 1.5 mcg/kg IV up to a maximum of 3 mcg/kg. No fentanyl after induction.
Propofol – standard dosage titrated to effect

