Rocuronium – standard dosage

Maintenance: Randomization to 3 groups, with infusion begun after induction while the patient is being prepped. Infusions to run until cardiologist informs anesthesiologist that no further ablations will be performed. Infusions will be prepared by the hospital pharmacy.

- Group 1: Placebo (0.9% NaCL)
- Group 2: Remifentanil 0.25 mcg/kg/min
- Group 3: Remifentanil 0.5 mcg/kg/min

Sevoflurane end-tidal concentration 1 to 4% (equivalent to 0.5 to 2 MAC)

Rocuronium – standard dosage

Ondansetron 0.1 mg/kg following last ablation

Emergence: Prior to emergence from anesthesia, the catheter access sites will be infiltrated with lidocaine as is the usual practice, the catheters removed, muscle relaxation reversed, and the patient allowed to awaken normally from anesthesia. The headphones and probe cap will be removed from the subject's head prior to emergence from anesthesia. The BIS sensor will be removed just before or just after emergence from anesthesia.

The only substantive difference between the study protocol and standard clinical care is the administration of remifentanil. Intravenous opioids are typically not given beyond induction of general anesthesia nor during catheter ablation of the arrhythmia. In this study, there is no reduced pain control than normal.

After the Procedure:

In the recovery room, before the subject is discharged from the hospital, a Post-Operative Questionnaire (Appendix C) will be performed in which the subject is asked about the last thing they remember before going to sleep, the first thing they remember upon waking up, and whether they have any memories or were dreaming during the procedure. If the research team is unable to administer the Post-Operative Questionnaire prior to the subject being discharged from the hospital, the subject will be contacted by telephone to complete this.

Additionally, information pertaining to the study will be collected from the electronic medical record. This information will include data from the pre-operative evaluation, electrophysiology procedure, anesthesia administered, and the recovery period.

b. Patient Selection and Inclusion/Exclusion Criteria

Inclusion Criteria:

12-30 years of age

Scheduled for electrophysiology procedure (EP) under general endotracheal anesthesia

Structurally normal heart by echocardiography

Right-handed

Exclusion Criteria:

Structural heart disease
Left handed
Unable to cooperate or understand the nature of the study

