optical contact with the scalp. The optodes are contained within a cap which will be placed on the patient's head in the catheterization laboratory. The light passes harmlessly through the subject's scalp onto the brain surface and returns, with some attenuation, to the detector optodes. The returning light yields information about blood-oxygenation levels in that region of the brain. The probe cap is not constricting and any discomfort will be minimized by surrounding the optodes with foam tape and using soft cloth straps against the head and face. After initial positioning, the probe may need to be shifted slightly until adequate signal is obtained through all detector fibers. In some cases, hair will be parted in order to achieve better optical contact. There will be no shaving of hair.

Prior to induction of general anesthesia, baseline activation signals of the somatosensory cortices and prefrontal cortices will be obtained in response to finger-tapping and brush stimuli applied to the dorsum of the hand as described above. This will provide baseline information to compare to the signals obtained during the procedure from surgically-induced pain.

In order to activate the Supplemental Motor Area, which should be quiet unless patients move, headphones will be placed on the subjects and an audio recording will be presented to subjects. The prompt will request that the subject imagine squeezing a tennis ball in their right hand, in a clasping motion, without actually performing the action. During this we expect SMA activity to occur if the subject is consciously aware based on similar results from prior studies. The audio stimuli will be presented to the subject every half hour throughout the procedure.

2. Patients will be randomized into one of three groups to receive an infusion which will be started after induction of general anesthesia while the patient is being prepped.

Group 1: 0.9% NaCl infusion

Group 2: Remifentanil 0.25 mcg/kg/min infusion

Group 3: Remifentanil 0.5 mcg/kg/min infusion

The infusions will be prepared by the hospital pharmacy. Investigators performing analysis of the NIRS signals will be blinded to the infusion the patient received. Infusions will be stopped after the cardiologist informs the anesthesiologist that no further ablations will be performed.

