The only substantive difference between the study protocol and standard clinical care is the administration of remifentanil. Intravenous opioids are typically not given beyond induction of general anesthesia nor during catheter ablation of the arrhythmia.

e. Definition of Primary and Secondary Outcomes/Endpoints

Primary Outcomes:

The primary outcome is the use of NIRS to measure/detect hemodynamic activations in the bilateral somatosensory cortices and the prefrontal cortices in response to the noxious stimulation

(pain) associated with catheter ablation of arrhythmias, and whether these activations are reduced or eliminated by remifentanil.

Secondary Outcome:

The secondary outcome is the use of NIRS to measure hemodynamic activation in the supplemental motor area to actual or intended movement either spontaneously, in response to pain, and/or in response to auditory stimuli.

f. Data Collection Methods, Assessments and Schedule (what assessments performed, how often)

The study will consist of enrollment and a Preoperative Questionnaire at the pre-catheterization work-up, the study protocol during two days if the patient is discharged the same day of the procedure, or three days if the subject is admitted overnight.

Prior to Preoperative Visit:

- Assessment of eligibility criteria

Pre-Operative Visit:

- Presentation of research study, informed consent/assent (20 minutes)
- Preoperative Questionnaire if patient/parents consent/assent (10 minutes)

Day of Procedure:

1) Before Procedure

- Equipment setup (20 minutes). Test run of brush and audio stimuli (10 minutes).
- BIS sensor applied to patient.

2) During Procedure

- Infusion of NaCL or remifentanil started after induction of anesthesia.
- Audio stimuli (5 seconds each) presented to the patient every half an hour.
- Electronic anesthesia record will capture relevant anesthetic and physiologic data. Study Coordinator and/or Research Nurse will document time and duration of ablations, times of catheter insertion and removal, and assure safety of the patient
- An investigator will operate the NIRS equipment.
- NIRS cap with optodes will be removed from the patient just prior to emergence from anesthesia.
- Average duration of an electrophysiologic study with catheter ablation of arrhythmias is 3 to 4 hours.

3) After Procedure

- Postoperative Questionnaire (10 minutes) will be administered before subject is discharged from the hospital, either on the day of or day following the procedure.

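### The only baselines named for the ablation signal are recorded before induction, so the within-subject comparison changes anaesthetic state together with stimulus

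*Combined protocol and SAP*

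**What the plan says.** Section 4.a (Day of Surgery, before the procedure) describes cap placement and then four pre-induction runs: rest, audio, finger tapping and brush. The cap goes on "Following light sedation with midazolam and prior to induction of general anesthesia", so every run is recorded in a lightly sedated, unanaesthetised subject. The list is introduced as a check of optode placement and signal quality. Of the resting run, however, it adds: "This baseline data will be used to compare changes observed during the catheterization procedure". Finger tapping and brush each carry the same condition: "This will only be conducted if time permits".

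Section 4.d states without that condition: "Prior to induction of general anesthesia, baseline activation signals of the somatosensory cortices and prefrontal cortices will be obtained in response to finger-tapping and brush". It gives the purpose: "This will provide baseline information to compare to the signals obtained during the procedure from surgically-induced pain". Section 4.f schedules a "Test run of brush and audio stimuli (10 minutes"); finger tapping is not listed, and brush is not marked optional.

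During the procedure (section 4.a), induction uses fentanyl, propofol and rocuronium. Maintenance is sevoflurane at 0.5 to 2 MAC with rocuronium and the randomised infusion, which starts after induction. The primary outcome (4.e) has two parts: whether NIRS detects activation in response to ablation, and whether remifentanil reduces or eliminates it. The Data Analysis Plan (5.c) says analysis is first within subject and then averaged across subjects. It defines no baseline window, no contrast and no rule for missing runs.

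**The concern.** A baseline comparison isolates a response only if the baseline differs from the response period in the stimulus alone. Here the named baselines also differ in anaesthetic state. An analyst who follows sections 4.a and 4.d as written would obtain a difference that general anaesthesia could produce, enlarge or hide, and could not say how much of it was the response to ablation.

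At stake is the detection half of the primary outcome. Randomisation does not protect it, because it is a within-subject question. The disagreement between sections adds a smaller problem: two of the named comparators may not exist for every subject, and no rule says what happens then.

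**Working it through.** **1. Is the sample size involved?** Inputs from section 5.d: pilot mean −3.764×10⁻⁷, SD 2.135×10⁻⁷, null mean zero, power 90%, usable-data rate 45%.

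- Effect size: 3.764 / 2.135 = 1.763, as stated.
- Alpha and sidedness are not given. Assuming two-sided 0.05, an exact two-sample t calculation gives 8 per group (power 0.906), which matches the plan's eight. A one-sample t test against zero would need 6.
- Enrolment: 8 / 0.45 = 17.8, so 18 per group; 3 × 18 = 54.

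The plan's figures reproduce, and nothing from the awake runs enters them.

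**2. The recordings side by side.**

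| Recording | Stimulus | State | Named as a comparator? |
|---|---|---|---|
| Rest, about 200 s | none | light midazolam, before induction | yes (4.a) |
| Finger tapping, brush | motor or innocuous | light midazolam, before induction | yes (4.d) |
| Interval just before each ablation | no ablation | sevoflurane, infusion running | no |
| Ablation | noxious | sevoflurane, infusion running | signal of interest |

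Each comparison that the text names moves from one of the first two rows to the last, so stimulus and state change at once. The third row would change the stimulus alone. It is recorded but never named. No innocuous run under anaesthesia is described.

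**3. What the resting comparison estimates.** Let *b* be the signal level without ablation and *r* the response to ablation.

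- Against awake rest: (b_anaesthetised + r) − b_awake = r + (b_anaesthetised − b_awake).
- Against a same-state window: (b_anaesthetised + r) − b_anaesthetised = r.

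The extra term is not estimated anywhere in the plan, and more subjects do not shrink it. Band-pass filtering (5.c) may remove a constant offset, but the cut-offs are not given. If the offset is removed, the comparison of levels carries little information; if it is kept, the comparison is confounded.

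For tapping and brush, the comparison is of one evoked response with another, so an offset is not the difficulty. The two responses still differ in both stimulus and state, and the difference cannot be divided between them.

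**4. The randomised contrast.** The infusion starts after induction, so every named baseline precedes it. If activation is scored from the awake baseline, that baseline cancels between groups in expectation, and remifentanil minus placebo equals:

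(r_remifentanil − r_placebo) + (b_anaesthetised,remifentanil − b_anaesthetised,placebo).

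The second term is any effect of remifentanil on the signal level apart from ablation. Its size is not in the documents. With a same-state window it drops out.

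**5. Missing tapping or brush runs.** No completion rate is given. Taking 90%, 75% and 50% as assumptions, with 8 usable sets per group:

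- Complete pairs, rounded down: 8 × 0.90 = 7.2, so 7; 8 × 0.75 = 6; 8 × 0.50 = 4.
- Chance that all 8 have the run, if independent: 0.90⁸ = 43%; 0.75⁸ = 10%; 0.50⁸ = 0.4%.

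Full completion would leave steps 2 and 3 unchanged.

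**The case against.** The strongest reply is that these comparisons feed no test. Section 5.c names no contrast of awake with anaesthetised data and ties the expected oxyhaemoglobin changes to stimulus onsets and offsets, which suggests an event-related analysis. Section 4.a introduces the runs as signal checks and 4.f calls them a test run. The sample size ignores them, and all randomised groups share one anaesthetic technique.

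Much of this stands, and it limits the point. It does not remove it: two sections give the runs a comparator role in plain terms, and 5.c names no other baseline.

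Several stronger readings are tempting, but the documents do not support them:

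- *The comparator is missing for some subjects, and for a non-random subset.* The text shows only that tapping and brush may be missing. Nothing links available time to the NIRS response. The resting run is not optional.
- *None of the difference is due to noxious input.* Confounding means that the noxious part cannot be separated, not that it is zero.
- *Baseline and ablation lie 3 to 4 hours apart.* That is the average procedure duration in 4.f, not this interval.
- *Propofol and fentanyl run during ablation.* Both are listed at induction only, with no fentanyl afterwards.
- *Relative concentrations rule out reading any response.* They do not prevent measurement of an evoked change within a segment; the difficulty applies to levels compared across segments.
- *The randomised comparison is biased.* This holds only under the scoring in step 4 of the working, which the plan neither adopts nor excludes.
- *The awake runs should not be compared with anything.* They can still be useful for localisation or as a descriptive reference.

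**Conclusion.** The point holds for the within-subject question. The baselines that sections 4.a and 4.d name cannot isolate the response to ablation, and the plan names no baseline that can. The size of the distortion cannot be estimated from the documents, because they give neither the effect of anaesthesia on the signal nor that of remifentanil. The sample size of 8 usable and 18 enrolled per group, 54 in total, is untouched. The randomised contrast is exposed only if activation is scored from the awake baseline.

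The conclusion assumes that the comparator sentences mean what they say. If the intended analysis is already event-related within the anaesthetised recording, the defect lies in the text, and the same correction settles it. The contradiction over tapping and brush stands in either case. The point should be addressed before analysis.

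**What to change.** In sections 4.a, 4.d and 5.c:

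1. State that activation for the primary outcome is measured against a fixed window just before each ablation onset, on the same channel and in the same anaesthetic state. Give the window length, and say how it is handled when it overlaps the response to a preceding ablation.
2. State that the awake resting, tapping and brush runs serve as signal-quality, localisation or descriptive reference data, and are not the inferential baseline for the ablation response.
3. Reconcile 4.a, 4.d and 4.f on which pre-induction runs are required and which are optional, and say how a missing run is reported.

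No new data are needed. NIRS is recorded throughout the procedure (4.a), and the time and duration of ablations are documented (4.f). The cost is a small amount of wording and analysis code.
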